The Effect of Different Exercise Types on Migraine Frequency in Individuals with Migraines

NCT05568004

Migraine is a neurological disorder characterized by recurrent, throbbing headache attacks and accompanying symptoms, associated with significant loss of quality of life and workforce. The diagnosis of migraine is made by anamnesis. Diagnostic criteria of the International Classification of Headache (ICHD-3 beta) published in 2013 are used for diagnosis. According to the World Health Organization (WHO), migraine is ranked as the third most common medical condition in the world and the second most common neurological disorder that causes disability. The one-year prevalence of migraine in the general population is 12%. In a large population-based epidemiological study, the frequency of migraine in our country was found to be 16.4%. Migraine is 2-3 times more common in women than men. Headache in migraine comes in attacks, the frequency of attacks varies from person to person and may be different in the same person. Neck pain is also observed during migraine attacks in approximately 75% of patients. In about one-third of individuals with migraine, reversible neurological symptoms (migraine aura) may occur, usually before the onset of pain. Aura symptom is more than 90% probable visual complaints. Chronic migraine (CM); It was defined as headaches that lasted more than 15 days a month for at least 3 months and at least 8 of the attacks met the criteria for migraine headache. It is estimated that CM has a frequency of 1-3% in the society and constitutes more than 10% of all migraine patients. CM includes patients with headache-related disability, loss of work force, overuse of medication, and marked deterioration in quality of life. CM is responsible for approximately 1% of disability worldwide and is among the major disabling diseases according to life-year-based assessments. Headache attacks in CM adversely affect the patient's work life, education, academic and social life. Numerous studies with the standardized Migraine-Specific Quality of Life Questionnaire and Migraine-Related Disability Questionnaire (MIDAS) have shown that CM is associated with significant work loss. In the International Burden of Migraine Disease (IBMS) study, more than half (57%) of CM patients reported that they were absent from work or school for 5 or more days in a three-month period, while 58% stated that they had difficulty in housework. Although the pathophysiology of CM and the mechanism of conversion to CM are not fully understood, atypical pain processing, central sensitization, cortical hyperexcitability and neurogenic inflammation are emphasized. MIDAS scores were found to be higher in patients with CM compared to those with episodic migraine (EM, headache less than 15 days a month) and the limitation was 2 times higher. The reason for this is that the number of painful days in CM is high, the number of comorbid diseases is high, and psychiatric and chronic pain syndromes are more associated with CM. Depression; It is the most common psychiatric comorbidity in CM (8.6-47.9%), and the migrainedepression relationship is bidirectional. Migraine is associated with a 2.5-fold increase in lifetime risk of depression. Depression is reported more frequently in migraine and CM patients with aura, and depression is one of the known risk factors for chronicity of migraine. Depression in CM is accepted as a poor prognosis indicator. The close relationship between anxiety disorders and migraine has been demonstrated in population and clinical studies . General anxiety disorders, obsessive compulsive disorder and panic disorder are 2-5 times more common in CM. Anxiety disorders are more common in CM than in EM cases (30.2% and 18.8%, respectively), and anxiety disorder is a risk factor for CM. Physical Activity is bodily movements that occur with the contraction of skeletal muscles and result in energy expenditure. Exercise is planned, structured, repetitive body movements to increase or maintain physical fitness. Exercise; can be

grouped under three groups as aerobic exercise, anaerobic exercise and flexibility, coordination and relaxation exercises. Aerobic exercises are low-intensity exercises (walking fast, running, cycling, etc.) in which the muscular activity energy required to perform the movement is produced by the system using oxygen. Anaerobic exercise is a medium and high intensity exercise (resistance exercises, etc.) aimed at increasing muscle strength in the foreground, in which the energy to be produced in order to perform the movement with muscle contractions is produced without the use of oxygen or by using a very small amount of oxygen. Several large population-based studies have concluded that low levels of physical activity are associated with higher migraine prevalence and frequency. Conversely, higher physical activity levels were associated with reduced migraine headache frequency and less migraine-related disability. There are several studies in the literature investigating the effect of aerobic exercise on the frequency of headaches in migraine patients. Varkey et al. showed that exercise capacity can be improved, frequency and severity of migraine attacks can be improved safely without worsening migraine symptoms, with a 12-week, 3 times a week, aerobic exercise program consisting of warmup and cool-down periods for untrained migraine patients. In the systemic review and meta-analysis (consisting of five randomized controlled and one clinical controlled studies), which included all studies in the literature investigating the effect of aerobic exercise on migraine, published in 2018, a significant reduction in the number of days with migraine in favor of the exercise group was found at the end of 10-12 weeks. CM patients were evaluated in only one of these studies, while EM and CM patients were included together in the others. When the literature is examined, aerobic exercise programs were previously performed by Varkey et al. It consisted of different types (walking, cycling, jogging, cross training including a combination of all) similar to the exercise protocol that has been shown to be safe and effective in migraine patients. No side effects related to aerobic exercise have been reported in the literature. In studies, the effects of aerobic exercise on migraine were frequently evaluated through migraine diaries. The mechanism of action of exercise is explained in two ways, biological and psychological. Biological mechanisms include the decrease in the amount of inflammatory markers (CRP, CGRP, Substance P, etc.) that are detected to be high in migraine patients as a result of regular aerobic exercise, increase in β -endorphin levels, which were previously shown to be low in migraine patients, with exercise, suppression of neurological inflammation by exercise, and neurovascular improvement. Among the psychological mechanisms, the increase in self-efficacy brought by exercise, the reduction of depression and anxiety symptoms that often accompany migraine, and its effects on mood and sleep are at the forefront. There are not enough studies in the literature investigating the effects of non-aerobic exercise types on migraine. There is a study evaluating the effect of yoga on migraine, and this study showed a significant decrease in migraine frequency in the yoga group. There is no study in the literature investigating the effect of resistance exercises on migraine. In studies in the literature, in which the effects of this group of exercises were evaluated, participants with headaches (including other pathologies besides migraine) were evaluated, and neck and shoulder exercises showed a reduction in headache and neck pain. Successful results have been obtained in studies on chronic pain syndromes using anaerobic (resistance) exercise in the literature. Considering that migraine headache is often accompanied by neck pain and chronic pain syndromes are common in this patient group, besides the direct effect of aerobic exercise on migraine frequency, by adding neck and shoulder resistance exercises to aerobic exercise, indirect effects of resistance exercise can also be observed. The research aimed to evaluate the effect of different exercise methods on the frequency of migraine attacks in participants between the ages of 18-50 who were diagnosed with chronic migraine according to the International Classification of Headache Disorders, 3rd edition (ICHD3beta), by a specialist neurologist. For

this purpose, a total of 90 people will be included in the study and three groups will be formed. Combined exercise consisting of aerobic and resistance exercises will be given to the first group, only aerobic exercise will be given to the second group, and the third group will be the control group. The aerobic exercise content is the same in the combined (first group) and isolated aerobic exercise group (second group), for a total of 45 minutes 3 days a week; It will consist of 15 minutes of warming up, 5 minutes of cooling down, 25 minutes of aerobic heart rate (60-80% of the maximum heart rate) at the same metabolic equivalent and with the same energy expenditure, cycling / brisk walking / jogging (low tempo jogging) exercises. Exercise groups will be shown face-to-face in detail before the study, and then the patients will be followed up at regular intervals with appropriate communication tools (phone, mail, etc.). Exercise intensity will be regulated using the perceived effort level (Borg Rating of Perceived Exertion Scale, RPE). During warm-up and cool-down, exercise intensity will be adjusted to be between RPE 11-13, and during aerobic exercise, RPE will be set to be between 14-16. In the combined group (first group), 3 sets x 12 repetitions gradually, after 2 sets x 8 repetitions in the first 2 weeks, using the resistance band (theraband) on other 3 days of the week, every other day; There will be five different resistance exercises(Craniocervical flexion-cervical retraction, reverse flies, shrugs, frontal rise, lateral rise) targeting the neck, upper back and shoulder muscles. Resistance exercise intensity will be adjusted using the OMNI-resistance exercise scale (keeping it between 6 and 8 on the scale). The third group will be asked to continue their normal lives. The exercise will take a total of 12 weeks. After the exercise, an 8-week follow-up period was planned to evaluate the continuation of the exercise effect. Patients will be asked to keep migraine diaries containing the frequency, severity, and duration of migraine attacks for at least 4 weeks before exercise, during 12 weeks of exercise, and during the 8week follow-up period after exercise. The change in the number of days with migraine (in migraine frequency) will be evaluated as a primary outcome measure. Headache severity based on migraine diaries as a secondary measure. At the end of the follow-up period, the surveys will be repeated. Astrand submaximal bicycle ergometer test will be used to measure aerobic capacity. At the end of this process, the effects of combined exercise and isolated aerobic exercise on migraine in patients with chronic migraine will be investigated compared to the control group. In addition, the positive effects of exercise on diseases such as anxiety and depression, which are frequently associated with migraine, and its effects on body aerobic capacity will also be evaluated in the study. Participants will be administered the Hospital Anxiety and Depression Scale(HADS) to compare their anxiety and depression levels, the Migraine Disability Assessment Scale(MIDAS) to assess migrainespecific quality of life, and the International Physical Activity Questionnaire(short form)(IPAQ-short) to compare physical activity status at baseline, at 12 weeks and at the end of the follow-up period Aerobic capacity will be measured indirectly with a bicycle ergometer. This method is the Astrand test, which is a 6-minute cycling test. Pedal resistance is adjusted to be 0.5-1 watt/kg. The speed is adjusted to 60 pedal cycles per minute. Heart rate tracking is measured by a heart rate monitor. The test is terminated when the desired heart rate is reached in the 6th minute. Calculating from the values, aerobic capacity is found

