# The Effect of Different Exercise Types on Migraine Frequency in Individuals with Migraine

[NCT05568004](#)

This is the preplanned and the primary analysis of these data. There were no missing data. Statistical analysis was conducted by a researcher blinded to the participants' groups using the Statistical Package for Social Sciences (SPSS) version 26.0 (IBM Corp., Armonk, NY, USA). The Shapiro–Wilk test and histograms evaluated the data for normal distribution, and the Levene test confirmed homogeneous variances between groups ( $p > 0.05$ ). Continuous data following a normal distribution are presented as mean  $\pm$  standard deviation (SD). The independent samples t test or Mann–Whitney U test was used to compare independent continuous data between groups, while the chi-square or Fisher's exact test was used to compare categorical data. Friedman two-way ANOVA was used to analyze dependent variables, while the two-way mixed ANOVA was used to examine the changes between groups over time. Before the two-way mixed ANOVA, boxplot evaluation confirmed no outliers. Mauchly's sphericity test showed that the assumption of sphericity for two-way interaction was met. Tukey's correction was used for pairwise subgroup comparisons. A  $p$ -value of  $< 0.05$  was considered statistically significant for all analyses.

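### The documents do not say how, or when, participants are allocated to the three groups, and the analysis of change in migraine days names no baseline covariate

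*Protocol*

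**What the plan says.** The protocol's design text (unnumbered) gives the whole account of group formation in one sentence: "a total of 90 people will be included in the study and three groups will be formed". It then describes the arms. The first receives combined exercise, "only aerobic exercise will be given to the second group, and the third group will be the control group". Of the controls it says "The third group will be asked to continue their normal lives". No assignment method, ratio, sequence, concealment or timing is given. Randomisation is mentioned only in the background, for a cited meta-analysis: "consisting of five randomized controlled and one clinical controlled studies".

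The outcome is defined as follows: "The change in the number of days with migraine (in migraine frequency) will be evaluated as a primary outcome measure". Its source is the participant's own diary: "Patients will be asked to keep migraine diaries containing the frequency, severity, and duration of migraine attacks for at least 4 weeks before exercise".

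The SAP says that a t test or Mann-Whitney U test "was used to compare independent continuous data between groups". It adds a two-way mixed ANOVA for change between groups over time, and Tukey's correction for pairwise comparisons. It names no covariate. It describes the analyst as blinded to group and says nothing about allocation.

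**The concern.** The trial asks whether exercise changes migraine frequency. Participants know whether they are exercising, and they record the outcome themselves. How they came to be in their group, and whether the baseline diary was complete by then, therefore matters a good deal for reading the result. The documents leave both open.

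The analysis offers limited protection if the groups start at different levels. A group that enters with more migraine days will tend to show a larger fall even if exercise does nothing, because high counts drift back towards the average. A comparison of raw change counts that drift as effect. A model with the baseline count as covariate allows for it. The baseline count is already collected but is not used in that way.

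**Working it through.** The plan contains no figure to reproduce: there is no effect size, SD, power or arm size. The calculation below shows how large the problem could be. It does not estimate an actual bias.

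**Inputs from the documents:** 90 participants, three groups, primary outcome a change in migraine days (Protocol); significance threshold 0.05, Tukey for pairwise comparisons, no covariate (SAP).

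**Assumptions:** equal arms, 90/3 = 30 each; two-sided tests; normal data; the same SD at baseline and follow-up (set to 1); correlation ρ = 0.5, with a range of 0.3 to 0.7; no true effect; expected baseline gap g of 0.3 to 0.5 SD between two arms; both arms regress towards a common mean.

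**1. Spurious difference in change.** Bias = (1 − ρ) × g.
- g = 0.3: 0.5 × 0.3 = 0.15 SD
- g = 0.5: 0.5 × 0.5 = 0.25 SD

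**2. Standard error of the difference in change.** √(2 − 2ρ) × √(2/30) = 1 × 0.258 = 0.258. The noncentrality is 0.15/0.258 = 0.58 and 0.25/0.258 = 0.97.

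**3. Critical values.** An unadjusted t test has 58 df and a per-comparison level of 5%. For Tukey with three groups and 90 − 3 = 87 df, the studentized range point is 3.37. Dividing by √2 gives 2.38, a per-comparison level of 1.9%.

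**4. False-positive rate for one pairwise comparison (noncentral t).**

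| ρ | g | Bias (SD) | Unadjusted t (nominal 5%) | Tukey (nominal 1.9%) |
|---|---|---|---|---|
| 0.3 | 0.3 | 0.21 | 10.4% | 4.9% |
| 0.3 | 0.5 | 0.35 | 20.3% | 11.3% |
| 0.5 | 0.3 | 0.15 | 8.8% | 4.0% |
| 0.5 | 0.5 | 0.25 | 15.9% | 8.3% |
| 0.7 | 0.3 | 0.09 | 7.3% | 3.2% |
| 0.7 | 0.5 | 0.15 | 11.4% | 5.6% |

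**5. What the covariate does.** Under the same assumptions, expected follow-up given baseline is the same in both arms, so the baseline-adjusted difference has no bias from the gap. Error variance falls from 2(1 − ρ) to 1 − ρ², a ratio of (1 + ρ)/2.
- ρ = 0.3: 0.65, a 35% reduction
- ρ = 0.5: 0.75, a 25% reduction
- ρ = 0.7: 0.85, a 15% reduction

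**6. How large a gap chance alone gives.** If allocation was random, the standard error of the baseline difference is √(2/30) = 0.258 SD. A gap of 0.3 SD is then 0.3/0.258 = 1.16 standard errors, and a gap of 0.5 SD is 1.94. The first would be unremarkable and the second uncommon.

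**The case against.** The strongest reply is that silence is not a design. A reader might infer that the trial is non-randomised, that willing exercisers chose the exercise arms, and that no difference could be attributed to exercise. The documents do not support this. The sentence on forming groups fits random or non-random assignment, and no text describes self-selection. The protocol is brief and mostly background. What stands is that the method, concealment and timing are not stated.

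A reader might also infer from "Exercise groups will be shown face-to-face in detail before the study" that participants knew their group while keeping the baseline diary. The sentence more naturally means instruction before the 12-week programme: the people shown are already in exercise groups, and remote follow-up comes next. Nothing places the instruction before or during the diary, so this point does not rest on it.

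Third, the analysis does use the baseline. The outcome is a change, and the mixed ANOVA examines change by group over time, so constant differences between groups drop out. That is correct, and it limits the point to regression to the mean and precision. The SAP's Tukey rule also lowers the false-positive rates, which is why both sets are shown.

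Finally, under random allocation the change comparison keeps its nominal level on average over possible allocations. The rates in the table describe a gap in expected baseline. With random allocation, the case for the covariate is the gain in precision and protection against a chance imbalance.

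**Conclusion.** The point holds in a limited form. Allocation method, concealment and timing are missing from both documents, and the analysis of the primary outcome names no baseline covariate. The first is a gap in reporting and does not show that allocation was poor. The second is a weakness with an inexpensive remedy.

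At correlation 0.5, a baseline gap of 0.3 to 0.5 SD gives a false difference in change of 0.15 to 0.25 SD. The per-comparison false-positive rate is then about 9 to 16% against 5% unadjusted, or about 4 to 8% against 1.9% with Tukey. Whatever the allocation, baseline adjustment would cut the error variance of a change comparison by about 15 to 35% at correlations of 0.7 to 0.3.

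All these figures rest on the assumed arm sizes, correlations and gaps, and the bias figures also on regression to a common mean. If allocation was not random and the groups have different stable levels, that last assumption fails and baseline adjustment alone would not secure a causal reading.

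**What to change.** - Make the primary analysis an ANCOVA, or a mixed model, of migraine days with baseline diary migraine days as a covariate. Keep the Tukey pairwise comparisons.
- State how participants were allocated, whether allocation was concealed, and when it took place relative to the baseline diary, as actually carried out. No particular randomisation scheme need be prescribed.
- If allocation was not random, say so, describe the conclusions as associations, and also adjust for baseline IPAQ and HADS.

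The cost is a few sentences and one further model fit. The diary, IPAQ and HADS are already collected at baseline, so no new data are needed. The SAP is written in the past tense and reports on the data, so if the adjusted analysis is added after results have been seen, it should be labelled as such and shown beside the analysis already specified.

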# The Effect of Different Exercise Types on Migraine Frequency in Individuals with Migraine

[NCT05568004](#)

This is the preplanned and the primary analysis of these data. There were no missing data. Statistical analysis was conducted by a researcher blinded to the participants' groups using the Statistical Package for Social Sciences (SPSS) version 26.0 (IBM Corp., Armonk, NY, USA). The Shapiro–Wilk test and histograms evaluated the data for normal distribution, and the Levene test confirmed homogeneous variances between groups ( $p > 0.05$ ). Continuous data following a normal distribution are presented as mean  $\pm$  standard deviation (SD). The independent samples t test or Mann–Whitney U test was used to compare independent continuous data between groups, while the chi-square or Fisher's exact test was used to compare categorical data. Friedman two-way ANOVA was used to analyze dependent variables, while the two-way mixed ANOVA was used to examine the changes between groups over time. Before the two-way mixed ANOVA, boxplot evaluation confirmed no outliers. Mauchly's sphericity test showed that the assumption of sphericity for two-way interaction was met. Tukey's correction was used for pairwise subgroup comparisons. A  $p$ -value of  $< 0.05$  was considered statistically significant for all analyses.

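### Does listing the Friedman test beside the mixed ANOVA, both at p < 0.05, leave the comparison with control undecided?

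*SAP*

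**What the plan says.** The SAP is one paragraph. For repeated measurements it says "Friedman two-way ANOVA was used to analyze dependent variables, while the two-way mixed ANOVA was used to examine the changes between groups" over time. It adds that Tukey's "correction was used for pairwise subgroup comparisons", and that p < 0.05 "was considered statistically significant for all analyses". For independent continuous data it also lists the t test or Mann–Whitney U. It attaches no test to a named outcome.

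The closing part of the protocol plans 90 people in three groups: combined exercise, aerobic exercise and control. The primary outcome is the change in days with migraine. The effects of the two exercise programmes "on migraine in patients with chronic migraine will be investigated compared to the control group". The next sentence adds an evaluation of "the positive effects of exercise on diseases such as anxiety and depression" and of aerobic capacity. Earlier in the same part, "an 8-week follow-up period was planned to evaluate the continuation of the exercise effect", and the three questionnaires are scheduled at baseline, week 12 and the end of follow-up.

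**The concern.** Two tests of repeated data stand in one sentence, share a threshold, and answer different questions. Friedman asks whether a set of people changed across visits. The mixed ANOVA interaction asks whether the arms changed differently. The SAP does not say which one supports a conclusion about exercise.

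The worry is strongest away from migraine days. The protocol names control explicitly only for effects on migraine. The aim on anxiety and depression names no comparator. The follow-up is said to assess whether the exercise effect continues, and the questionnaire sentence ends "to compare physical activity status at baseline, at 12 weeks and at the end of the follow-up period", which could be read as a within-person comparison over three visits. A literal reader might answer these aims with a within-arm p-value and call it significant.

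That would matter, because people enrolled with chronic migraine may improve in every arm. Entry depends on a headache-day threshold, and the protocol notes that attack frequency varies within a person, so some regression to the mean is plausible. A shared fall of that kind could be credited to exercise.

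**Working it through.** **What each test can see.** Friedman for *n* people and *k* visits uses only the visit rank sums R_j:

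Q = [12 / (n k (k+1))] Σ R_j² − 3n(k+1).

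With an assumed n = 30 in one arm and k = 3, this is Q = ΣR_j²/30 − 360, referred to chi-square on 2 df (critical value −2 ln 0.05 = 5.99). No group label enters, so any shift over time moves Q, whatever its cause.

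The group-by-time test uses the residual (cell mean − arm mean − visit mean + grand mean). Add a shift δ_t common to all arms at visit t, with average δ̄ over visits. The residual changes by δ_t − δ̄ − δ_t + δ̄ = 0. A fall shared by all arms cancels exactly. The degrees of freedom are (3−1)(3−1) = 4 and 3 × (30−1) × (3−1) = 174.

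**Simulation.** The protocol supplies only the 90 people and three groups. It gives no SD, correlation or power calculation, so there is no stated figure to reproduce. Assumed: 30 per arm, three visits, normal data with SD 1, equal correlation ρ between visits, and the same fall at both later visits in every arm, hence no exercise effect. There were 3,000 trials per setting. Percentage significant at 0.05:

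| ρ | Shared fall (SD) | Friedman, one exercise arm | Friedman, all 90 pooled | Group-by-time |
|---|---|---|---|---|
| 0.5 | 0 | 6.0 | 5.5 | 5.3 |
| 0.5 | 0.2 | 15 | 37 | 5.0 |
| 0.5 | 0.3 | 28 | 70 | 4.6 |
| 0.5 | 0.5 | 67 | 99 | 4.5 |
| 0.5 | 0.8 | 97 | 100 | 5.4 |
| 0.7 | 0 | 4.5 | 5.1 | 5.8 |
| 0.7 | 0.2 | 23 | 57 | 5.3 |
| 0.7 | 0.3 | 46 | 90 | 5.1 |
| 0.7 | 0.5 | 88 | 100 | 5.6 |
| 0.7 | 0.8 | 99.8 | 100 | 4.1 |

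The simulation error on a 5% rate is √(0.05 × 0.95 / 3000) = 0.4 percentage points, so the last column is consistent with 5%. A wider grid (ρ from 0.3 to 0.8, falls from 0 to 1 SD, 32 settings of 5,000 trials) gave 4.2–5.5% for the group-by-time test.

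Where there is a real shared fall, a significant Friedman test correctly rejects its own null of no change over time. It becomes a false positive only if it is read as exercise against control.

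**Does either document read it that way?**

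- *Roles.* The SAP sentence contrasts the tests: "Friedman two-way ANOVA was used to analyze dependent variables", while between-group change goes to the mixed ANOVA. The latter is not restricted to migraine days.
- *Follow-up.* The protocol describes diaries running through the 8 weeks and surveys repeated at their end. Only then does it place the comparison with control, at the end of that process. The natural reading is that the comparison covers follow-up.
- *Physical activity.* The three time points come at the end of a sentence about administering all three questionnaires. They read most naturally as the visit schedule. Three visits suit a mixed ANOVA as well as Friedman.
- *Anxiety and depression.* This aim directly follows the comparison with control, as an addition to it, in a trial that has a control arm. Not repeating the comparator is an omission of drafting.

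**The case for a change.** The best case for a change is that probable intent is not specification, and a SAP exists to remove this kind of doubt. It does not say whether Friedman is run per arm or pooled, whether it is a fallback for non-normal data, or whether the Tukey pairs are arms or visits. The t test and Mann–Whitney U are also left without a named outcome. Two or three sentences would settle all this at almost no cost.

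Those gaps are real, and the silence on Friedman's purpose stands as a minor reporting point. It does not amount to a defect. A rule making the mixed ANOVA decisive for every outcome might alter the analysis if Friedman had been the fallback for non-normal outcomes, which the SAP neither states nor excludes. Even on that reading Friedman could not stand in for a comparison of arms, and the SAP lists Mann–Whitney U as a between-group test. The SAP is also written in the past tense and reports that no data were missing, so added text would describe results rather than fix a rule in advance.

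**Conclusion.** The concern does not call for a change. It is right that Friedman has no group term and that its purpose is not spelled out. It does not show that the plan would reach a wrong conclusion. Followed as written, the SAP tests between-group change with the mixed ANOVA. That test holds 5% under any fall shared by the arms, given normal data and sphericity, which the SAP says were checked. The large Friedman percentages depend on assumed falls, correlations and arm sizes, and on a reading that neither document states. With no shared fall, Friedman itself stays at about 5%.

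An analyst will ordinarily present Friedman results as change over time, say whether they are per arm or pooled, and rest statements about exercise against control on a between-group test. This conclusion would change only if a report offered a within-arm or pooled Friedman p-value as evidence of an exercise effect.

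### Optional addition, not an error: the stated group-by-time test names no baseline covariate, and if allocation was random a labelled baseline-adjusted analysis costs little, for a precision gain that is unknown and may be nil

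*SAP*

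**What the plan says.** The SAP is a single statistical paragraph. Its test of differential change is stated as "the two-way mixed ANOVA was used to examine the changes between groups over time". It lists no covariate, no ANCOVA and no sensitivity analysis. The other tests it names for continuous data (t test, Mann–Whitney U, Friedman) take no covariate either. It calls itself the planned primary analysis, but it is written in the past tense and gives the outcome of its assumption checks. It reports no missing data.

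The Protocol has no section headings; its closing description of the design covers the rest. On the outcome: "The change in the number of days with migraine (in migraine frequency) will be evaluated as a primary outcome measure". Diaries are kept "for at least 4 weeks before exercise, during 12 weeks of exercise, and during the 8week follow-up period after exercise", so a baseline value exists for each participant. On the arms it says only that "a total of 90 people will be included in the study and three groups will be formed". Neither document says that this trial's allocation was random.

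The SAP does not list the levels of the time factor. Its remark that Mauchly's "sphericity test showed that the assumption of sphericity for two-way interaction was met" suggests three or more levels, and a change outcome implies that baseline is one of them. Both are inferences.

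**The concern.** If baseline is a level of the time factor, the interaction test treats it as an outcome. For one baseline and one follow-up, that amounts to subtracting the whole baseline value from the follow-up value. Subtraction is the most precise use of baseline only when the slope of follow-up on baseline is 1. For any other slope, estimating it by ANCOVA leaves less residual variance.

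The Protocol wants each exercise arm compared with control, and 90 people in three arms is 30 per arm if the split is equal. At that size a narrower interval is worth having when it needs no further patients or visits. What is at stake is the width of the intervals, not whether the stated test is valid.

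**Working it through.** The documents give no power, effect size, SD or correlation, so there is no figure of the plan to reproduce.

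**Inputs.**
- From the Protocol: 90 people, three groups, and a pre-exercise diary.
- Assumed: 30 per arm, random allocation, correlation r between baseline and follow-up, and k = follow-up SD / baseline SD.

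**Step 1: what the stated test does with baseline.** In simulated trials with one baseline, one follow-up, equal SDs and 3 × 30 people (3,000 runs per setting), the group-by-time test and the change-score test rejected equally often in every setting, for example 80.1% and 80.1% at r = 0.5.

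**Step 2: validity.** In the same simulations with no effect, the mixed ANOVA rejected in 4.6% to 5.2% of runs and ANCOVA in 4.3% to 5.3%. Both hold the 5% level.

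**Step 3: variance at one time point.** In units of the baseline variance:
- change score: 1 + k² − 2rk
- ANCOVA residual: k²(1 − r²)
- difference: (1 + k² − 2rk) − k²(1 − r²) = (1 − rk)²

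The difference cannot be negative, so the adjusted variance never exceeds the change-score variance. It is zero when rk = 1. Example: r = 0.5, k = 1 gives 0.75 / 1.00 = 0.75; r = 0.5, k = 2 gives 3.00 / 3.00 = 1.00.

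| Variance ratio, ANCOVA / change | k = 1 | 1.25 | 1.5 | 1.75 | 2 |
|---|---|---|---|---|---|
| r = 0.3 | 0.65 | 0.78 | 0.87 | 0.93 | 0.96 |
| r = 0.5 | 0.75 | 0.89 | 0.96 | 0.99 | 1.00 |
| r = 0.7 | 0.85 | 0.98 | 1.00 | 0.97 | 0.93 |

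**Step 4: cost of estimating the slope.** With 90 people in three arms, the average variance penalty is 1 + 1/(90 − 3 − 2) = 1 + 1/85 = 1.012.

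**Step 5: interval width.** Width ratio ≈ √(variance ratio × 1.012). At r = 0.5 this gives 0.87, 0.95, 0.99, 1.00 and 1.01 for k = 1 to 2. The best cell in the table gives √(0.65 × 1.012) = 0.81. With no gain at all, √1.012 = 1.006, which is 1% wider after rounding.

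**Step 6: outside the grid.** The table is not a set of bounds. With equal SDs, the variance ratio after the penalty is 0.96 at r = 0.9 and 1.002 at r = 0.98. With k = 0.75 and r = 0.3, it is 0.46 before the penalty.

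**Step 7: if allocation was not random.** The ANCOVA slope is rk, so the two estimates differ by (1 − rk) × the baseline difference between arms. For an assumed 2-day baseline difference, that is (1 − 0.5) × 2 = 1 day at rk = 0.5, and (1 − 0.75) × 2 = 0.5 day at rk = 0.75. The choice of method is then about what is being estimated as well as about precision.

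**The case against.** The strongest case against is that this is a preference between two valid estimators. The outcome is a change, the SAP tests change, and baseline is probably already in the model. All of that stands, so the point is offered only as an addition.

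Three further objections stand in part.
- The remedy depends on random allocation, which the documents do not state. It is therefore conditional.
- The SAP mentions no confidence intervals and does not say which comparisons Tukey's correction covers. The widths above are thus set against a change-score interval at one time point, which the SAP does not itself describe. Arm differences with intervals could be reported without a covariate; the covariate affects only their width.
- The time levels are assumed. With two follow-up times, an advantage of ANCOVA on their mean over the omnibus interaction test comes partly from averaging. At r = 0.9, simulated power was 83% for the interaction, 89% for the change in the mean and 91% for ANCOVA on the mean. That is why the working stays at a single time point.

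A reader might also infer more than the documents support.
- *That the SAP is wrong or ignores baseline.* The test holds its level, and the text suggests that baseline is a time level.
- *That the trial would gain confirmatory power.* The described analysis has already been run. An analysis added now is post hoc and can only sharpen the description of the differences.
- *That chronic-migraine entry truncates the baseline outcome at 15 days and so removes the gain.* The Protocol's figure of 15 belongs to "headaches that lasted more than 15 days a month for at least 3 months". Its migraine criterion is 8 and is worded as attacks, whereas the outcome is migraine days. The Protocol also says that "The diagnosis of migraine is made by anamnesis", and nowhere says that the baseline diary decides entry. Entry may restrict the baseline spread to some degree, but the documents do not show how much.

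**Conclusion.** The point holds as a low-cost improvement of optional priority, not as a fault in the SAP. Given random allocation, baseline adjustment at one time point cannot do worse than the change score, apart from a slope cost of about 1% of variance on average. Over the assumed grid the saving runs from 35% of the variance to nothing. Where this trial falls cannot be told from the documents, because it depends on an SD ratio and a correlation that are not reported. Equal arms, the time levels and the values of r and k are all assumptions. Without random allocation the precision argument lapses.

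**What to change.** 1. Keep the mixed ANOVA as the primary analysis, and list its time levels.
2. State how the three groups were allocated.
3. If allocation was random, add one supplementary analysis, labelled post hoc. Take post-baseline migraine days per 28 days as the outcome and baseline migraine days per 28 days as the covariate, by ANCOVA or a repeated-measures model of the post-baseline periods. The common scale is needed because the diary periods differ in length (at least 4, 12 and 8 weeks). Say which diary weeks make up each value.
4. Report Tukey-adjusted arm differences with 95% CIs at end of exercise and end of follow-up, together with the baseline and post-baseline SDs and their correlation, so that readers can judge the gain.
5. If allocation was not random, keep the change analysis and say that the two methods can estimate different quantities.

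The cost is one extra run in the same software and one post hoc analysis to disclose. It needs no new data or patients. At worst, the intervals are on average about 1% wider than change-score intervals.
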